3.3 Secondary objectives

- Generic and AF-specific patient-reported QoL using the SF-36 global and domain-specific scores, the AFEQT overall score and the EQ-5D-5L summary index and visual analogue scale at six and twelve months.
- Echocardiographic left-ventricular ejection fraction (LVEF) and diastolic function (E/e' and composite of diastolic indices) at twelve months.
- Functional assessment, including 6-minute walking distance achieved, change in European Heart Rhythm Association (EHRA) class and cognitive function at six and twelve months.
- Change in B-type natriuretic peptide (BNP) levels as a surrogate for total cardiac strain at six months.
- Change in heart rate from baseline and group comparison using 24-hour ambulatory ECG.

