8.1 Baseline Visit

The baseline visit will occur as soon as possible after screening and will involve the following procedures (see **Section 9** for procedure details):

- Verify inclusion/exclusion criteria.
- Obtain written informed consent from the potential participant.
- Randomise the patient via telephone or the secure web-based system as outlined in **Section 6**
- Administer QoL and functional capacity questionnaires.
- Review recent blood results (within 6 months of Baseline Visit)
 - Assessing renal function to aid in dose assignment and serum potassium level as part of standard clinical care.
- Document the use of oral anticoagulation and arrange appropriate prescription for patients not on therapy according to clinical guidelines. If the participant is already receiving vitamin-K antagonists (VKA), recent INR results will be documented.
- Record results of physical examinations.
- Collect blood samples for baseline blood tests and biomarker analysis.
- Complete case report form (CRF)
- Perform a 12-lead electrocardiogram.
- Supervise a 6-minute walk test, recording distance walked and peak heart rate.
- Arrange the baseline echocardiogram; images will be delivered to the echocardiographic core laboratory for blinded reporting.
- Discuss the randomised allocation with the participant including schedule for drug therapy and up-titration.

Participants will be followed up by telephone call two weeks after the Baseline Visit to ensure they have commenced trial medication.

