8.2 Up-Titration Visits

For the majority of participants, two up-titration visits will be planned to supervise the appropriate use of medications as per the up-titration schedule (see **Appendices A and B**). Additional up-titration visits, as required, are acceptable in order to attain a heart rate at rest of ≤ 100 bpm.

Up-titration visits will involve the following procedures:

- Record adverse events as reported by the participant or observed by the investigator.
- Review of medications and plan for trial drug up-titration
- Assessment of compliance
- Symptom-directed clinical examination
- Vital signs, including heart rate and blood pressure
- Administer QoL and functional capacity questionnaires (last up-titration visit only).
- Organise a 24-hour ambulatory ECG once up-titration completed (results to be forwarded to the clinician).

8.3 Visit 2, Month 6

Visit 2 will occur at an interval of six months (\pm four weeks) after the Baseline Visit and involve the following procedures:

- Administer QoL and functional capacity questionnaires.
- Record adverse events as reported by the participant or observed by the investigator.
- Confirm current rate control therapy (including dosage) and check concomitant medications.
- Assessment of compliance.
- Collect blood samples for biomarker analysis.
- Collect blood sample for serum digoxin concentration, potassium and creatinine as part of standard clinical care.
- Record time in therapeutic range for patients on anticoagulation with vitamin-K antagonists and compliance in patients receiving non-VKA oral anticoagulants.
- Obtain a twelve lead ECG.
- Record the results of physical examinations and vital signs.
- Supervise a 6-minute walk test, recording distance walked and peak heart rate.
- Complete other CRF requirements.
- If an echocardiogram has been performed for clinical reasons since the previous visit, images will be retrieved and sent to the core echocardiographic laboratory.

- Confirm appointment date for Visit 3.

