12.1.2 Secondary Outcomes

Patient-reported QoL:

- SF-36 global and domain-specific scores at 6 and 12 months
- EQ-5D-5L summary index and visual analogue scale at six and twelve months
- AFEQT overall score at six and twelve months

Cardiac function:

- Echocardiographic LVEF at 12 months
- Diastolic function (E/e' and composite of diastolic indices) at 12 months
- Functional assessment
- Six-minute walking distance at 6 and 12 months
- Change in European Heart Rhythm Association (EHRA) class at 6 and 12 months

Biomarkers:

- Change in B-type natriuretic peptide (BNP) levels at 6 months
- Change in heart rate using 24-hour ambulatory ECG

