9.6. Analysis methods – secondary outcomes

A template for reporting all the secondary outcomes is given in Appendix D6.

Patient-reported QoL

For the RATE-AF trial, questionnaires SF-36v2, EQ-5D-5L and AFEQT are administered at baseline, 6 months and 12 months.

Up-titration visits:

These questionnaires are also administered for each patient at their last up-titration visit.

Note: the data for last up-titration visit is not done at any scheduled time-point due to the fact that each patient will have different up-titration visits (i.e. some will have 6 and some may only have 1) and so for this reason the data collected for last up-titration visit will only be summarised by treatment arm and no formal analysis for this data will be conducted.

- **SF-36v2 global and domain specific scores at 6 and 12 months**

The data for these outcomes are continuous in nature and the computation for the global and domain specific scores is described in the data manipulations section 9.4. The mean and standard deviation along with minimum and maximum values for global and domain specific scores will be presented by treatment arm and time-point.

The global and domain-specific scores will be analysed separately at 6 and 12 months using the same analysis methods as described in section 9.5. for primary outcome:

- Physical component summary (PCS) score at 12 months
- Mental component summary (MCS) score at 6 months and 12 months
- Physical Function score at 6 months and 12 months

- Role Limitation Due to Physical Problems score at 6 months and 12 months
- Role Limitation Due to Emotional Problems score at 6 months and 12 months
- Social Functioning score at 6 months and 12 months
- Mental Health score at 6 months and 12 months
- Energy/Vitality score at 6 months and 12 months
- Pain score at 6 months and 12 months
- General Health Perception score at 6 months and 12 months

The range for each domain of the SF-36v2 is from 0=worst score to 100=best score. The Bisoprolol arm will again be used as a reference category for all model based analysis for SF-36v2 and so higher values will indicate better outcome for Digoxin arm.

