The data for the composite of diastolic indices is a binary (yes/no) and will be computed as described in the data manipulations section 9.4. This data is collected at baseline and 12 months and will be summarised as number and percentage by treatment arm and time-point. The analysis for this outcome will be conducted using a logistic regression model, where the outcome will be the binary category (yes/no) at 12 months and independent variables in the model being the baseline category, treatment arm, all minimisation variables, age at randomisation and baseline LVEF. An adjusted odds ratio and 95% confidence interval will be estimated from the logistic regression model.

- **Change in heart rate**

The data type for heart rate is continuous in nature. This data is collected at baseline, 6 months and at 12 months. The mean and standard deviation along with minimum and maximum values will be presented by treatment arm and time-point for 1) Radial heart rate, 2) Apical heart rate, 3) 12-lead ECG heart rate, and 4) 24-hour ambulatory average heart rate. The 24-hour ambulatory heart rate is only measured once and so no baseline score will be there to adjust for it in analysis.

These outcomes will be analysed using the same analysis methods as described in section 9.5 for primary outcome and analysis will be done separately for 6 and 12 month time-points.

A scatter plot of radial vs apical heart rate at each time point will be produced to visualise the radial-apical discrepancy.

Functional assessment

- **Six-minute walking distance at 6 and 12 months**

The data for this outcome is continuous in nature and this test is conducted at baseline, 6 months and 12 months. The time (measured in min/s) and distance (measured in metres) are only recorded if the patient did the test. Therefore this data will be summarised by treatment arm and time-point with respect to the number of patients conducting the test, the mean and standard deviation, median and IQR as well as minimum and maximum values for time and distance covered. Reasons for stopping the test prematurely were also collected and so this will also be summarised by treatment arm and time-point.

The main endpoint for this outcome is the distance (in metres) walked and so this will be analysed using the same analysis methods as described in section 9.5 for primary outcome and analysis will be done separately for 6 and 12 month time-point.

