Reference group for the treatment arm in the model is Bisoprolol arm

Higher values indicate better scores so a positive mean difference favours Digoxin arm

Diastolic function	Time point	Statistic	Digoxin	Bisoprolol	Logistic regression model	
					Adjusted Odds Ratio ¹ 95% CI	P-value ¹
Composite of diastolic indices	Baseline	No			-	-
		Yes				
	No					
	Yes					
		No				
		Yes				
Composite of diastolic indices	12 months	No				
		Yes				
	No					
	Yes					
		No				
		Yes				

1-Adjusted for treatment arm, baseline score, all minimisation variables, age at randomisation and baseline LVEF

Reference group for the treatment arm in the model is Bisoprolol arm

Higher values indicate better scores so an odds ratio >1 favours Digoxin arm

Change in heart rate

Secondary outcome	Time point	Statistic	Digoxin	Bisoprolol	Linear regression model	
					Adjusted mean difference ¹ 95% CI	P-value ¹
Radial Heart (bpm)						
Radial Heart rate (bpm)	Baseline	N Mean [SD] Min - Max			-	-
	6 months	N Mean [SD] Min - Max				
	12 months	N Mean [SD] Min - Max				
Apical Heart rate (bpm)						
Apical Heart rate (bpm)	Baseline	N Mean [SD] Min - Max			-	-
	6 months	N Mean [SD] Min - Max				
	12 months	N Mean [SD] Min - Max				
12-lead ECG Heart rate (bpm)						
12-lead ECG Heart rate (bpm)	Baseline	N Mean [SD] Min - Max			-	-
	6 months	N Mean [SD] Min - Max				
	12 months	N Mean [SD] Min - Max				
24-hour ambulatory average Heart rate (bpm)						
24-hour ambulatory Heart rate	24-hour	N Mean [SD] Min - Max				

¹-Adjusted for treatment arm, baseline score, all minimisation variables, age at randomisation and baseline LVEF

The Bisoprolol arm will be used as a reference category

Six-minute walking distance at 6 and 12 months

Six-minute walking test	Digoxin (N=)	Bisoprolol (N=)	Total (N=)
6 months follow-up			
Did the patient undergo the 6-min walk test? No Yes Missing			
If yes: Total time spent (min/s) Median {IQR} Min - Max Total distance covered (m) Median {IQR} Min - Max Was the test stopped prematurely? No Yes			
12 months follow-up			
Did the patient undergo the 6-min walk test? No Yes Missing			
If yes: Total time spent (min/s) Mean [SD] Median {IQR} Min - Max Total distance covered (m) Mean [SD] Median {IQR} Min - Max Was the test stopped prematurely? No Yes			

Distance covered (in metres) from the 6-minute walk test

Secondary outcome	Time point	Statistic	Digoxin	Bisoprolol	Linear regression model	

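### The ambulatory heart-rate outcome is labelled a change but rests on one on-treatment recording, and its between-arm analysis omits the baseline heart rate that the trial already collects

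*SAP*

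**What the plan says.** Protocol 3.3 states the secondary objective as "Change in heart rate from baseline and group comparison using 24-hour ambulatory ECG", and SAP 3 repeats it. The outcome lists in the protocol's Trial Summary, protocol 12.1.2 and SAP 4.4 shorten this to "Change in heart rate using 24-hour ambulatory ECG".

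The timing is in protocol 8.2: "Organise a 24-hour ambulatory ECG once up-titration completed". Protocol Table 1 and SAP Appendix C agree. The ambulatory row is blank at baseline and at month 12, marked at the up-titration visits and marked conditionally at month 6.

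SAP 9.6 groups four measures under change in heart rate: radial, apical, 12-lead ECG and 24-hour ambulatory average. It opens by saying that the data are collected at baseline, 6 and 12 months. It then makes an exception for the fourth measure: "The 24-hour ambulatory heart rate is only measured once and so no baseline score will be there to adjust for it in analysis". It closes by sending all of these outcomes to the section 9.5 model, run separately at 6 and 12 months. The Appendix D6 heart-rate table carries one footnote for all four measures: "Adjusted for treatment arm, baseline score, all minimisation variables, age at randomisation and baseline LVEF".

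Other heart rates do exist at baseline. Protocol 8.1 includes "Perform a 12-lead electrocardiogram", protocol 9.4 includes manual radial and apical rates, and SAP Appendix D2 tabulates all three at baseline.

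**The concern.** Heart rate is the most direct effect of the two drugs being compared, so a reader will look closely at this outcome. Two things are out of order.

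First, the outcome name promises a quantity that the schedule cannot supply. The analysis text and table footnote then give instructions (two time points, a baseline score) that cannot be carried out for this measure. An analyst would have to decide what to do after the data are in hand.

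Second, SAP 9.6 moves from the absence of an ambulatory baseline to no heart-rate adjustment at all. A baseline from the same method is not required for covariate adjustment. Any baseline variable that predicts the outcome improves precision, and entry heart rate is an obvious candidate. It is not a minimisation factor (EHRA class and gender are), so the design does nothing to balance it beyond randomisation.

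**Working it through.** **Can a change be derived?** A change needs two recordings by the same method, one before treatment. Protocol 8.2, Table 1, SAP Appendix C and SAP 9.6 all point to one recording, on treatment. So the quantity named in protocol 12.1.2 and SAP 4.4 cannot be calculated from ambulatory data.

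**What can be derived?**
- From ambulatory ECG: a difference between arms in on-treatment 24-hour mean rate. The D6 ambulatory row is already laid out this way, with one time point and no baseline line.
- From radial, apical and 12-lead ECG rates: follow-up values at 6 and 12 months, each adjusted for its own baseline.

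**Which covariates does the ambulatory model keep?** Removing the baseline score from the section 9.5 model leaves treatment arm, gender, EHRA class, age and baseline LVEF. No heart-rate variable remains.

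**The plan's own sample size.** The documents give no calculation for heart rate, so the quality-of-life calculation (protocol 12.2, SAP 4.7) serves as the yardstick: effect 0.5 SD, power 85%, two-sided alpha 0.05, 1:1 allocation.
- n per arm = 2 × (1.960 + 1.036)² / 0.5² = 71.8, so 72 per arm and 144 in total, as stated.
- 144 / 0.90 = 160, as stated.
- Power at 72 per arm is 85.1% by the normal approximation and 84.6% by the exact t calculation. The plan's figure reproduces.

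**What a baseline rate covariate would add.** Let r be the partial correlation between baseline heart rate and on-treatment ambulatory rate, given the covariates already in the model. The documents do not give r, so a range is shown. SD means the residual SD before the covariate is added, and 72 per arm are assumed to have a recording.
- Residual variance is multiplied by 1 − r².
- Confidence interval width is multiplied by √(1 − r²).
- Detectable difference at 85% power = (1.960 + 1.036) × √((1 − r²) × 2/72), in SD units.
- Equivalent unadjusted total N = 144 / (1 − r²).

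| r (assumed) | 1 − r² | CI width | Detectable difference (SD) | Power at 0.5 SD | Equivalent N |
|---|---|---|---|---|---|
| 0 (as planned) | 1.00 | 1.00 | 0.499 | 85.1% | 144 |
| 0.2 | 0.96 | 0.98 | 0.489 | 86.5% | 150 |
| 0.3 | 0.91 | 0.95 | 0.476 | 88.2% | 158 |
| 0.4 | 0.84 | 0.92 | 0.458 | 90.5% | 171 |
| 0.5 | 0.75 | 0.87 | 0.432 | 93.4% | 192 |
| 0.6 | 0.64 | 0.80 | 0.400 | 96.3% | 225 |

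The interval narrows by about 2% at r = 0.2 and 20% at r = 0.6. The documents give no SD for heart rate, so the gain cannot be put in beats per minute without inventing one.

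**The case against.** The strongest reply is that little is actually broken. The objective in protocol 3.3 can be read in two parts: a change from baseline, and a group comparison by ambulatory ECG. Protocol 9.10 restates the ambulatory objective purely as a comparison of heart-rate control between the arms. One on-treatment recording serves that, and the other three rates serve the change. SAP 9.6 openly discloses the missing baseline, the D6 row has a single time point, and SAP 9.1 limits baseline adjustment to where it is appropriate. All of this stands. It does not rescue the outcome lists, which tie change directly to the ambulatory ECG, or the SAP sentences that cannot be followed for this row.

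Three stronger readings are tempting, and the documents do not support them.
- **The objective cannot be met, or the trial will report a change that it never measured.** The comparison can be made, and the D6 template reports a between-arm difference for this row, not a change.
- **Chance imbalance in entry heart rate biases the comparison.** Under randomisation the unadjusted difference is unbiased. Chance imbalance is already part of its standard error, so this is the same precision loss counted again.
- **The variable recording time invalidates the comparison.** SAP 9.6 does say of up-titration visits that "some will have 6 and some may only have 1", but there it explains why questionnaires from the last such visit are only summarised. Completion of up-titration is a deliberate treatment-state anchor for the ECG.

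It is also fair that leaving out a surrogate covariate is a choice about precision, and that r may be low. Some patients may be on beta-blockers near entry (a subgroup in SAP 9.9), and protocol 8.2 allows extra titration visits towards a common resting-rate target. The low end of the range should be taken seriously.

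**Conclusion.** The point holds as a labelling and specification fault in one secondary outcome, together with an available gain in precision that the SAP does not take up. The label, the 6- and 12-month instruction and the baseline-score footnote are wrong for the ambulatory row on the documents alone, with no assumption needed. The gain, about 2% to 20% off the confidence interval width, rests on an assumed partial correlation of 0.2 to 0.6 and on 72 recordings per arm. The primary outcome, the sample size and the other three heart-rate measures are unaffected. It is worth correcting before analysis mainly because a covariate chosen in advance carries no suspicion of having been picked for its result.

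**What to change.** 1. In protocol 3.3, protocol 12.1.2, the Trial Summary, SAP 3 and SAP 4.4, describe the ambulatory outcome as on-treatment 24-hour mean heart rate, compared between arms. Keep change from baseline for the radial, apical and 12-lead ECG rates.
2. In SAP 9.6, state that the ambulatory mean is analysed once, as the D6 row already shows. Restrict the data-collection statement and the separate 6- and 12-month analyses to the other three measures.
3. In SAP 9.6, add baseline apical heart rate to the section 9.5 model for this outcome, in place of the missing baseline score. Name this one covariate only, with no option to switch to the ECG rate or to fill gaps from it. SAP 9.10 already uses it in a sensitivity analysis of the primary outcome, and SAP 9.6 already adds outcome-specific covariates for LVEF.
4. Give the ambulatory row its own D6 footnote listing the covariates actually used.

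The cost is one extra model covariate, and the new outcome wording has to be communicated as protocol 14.3 requires. Anyone without a baseline apical rate would drop out of an analysis of received data, and the documents do not say how many that might be. No new recording or visit is needed.

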9.7. Analysis methods – exploratory outcomes and analyses

Any data that does not form a pre-specified outcome will be presented using simple summary statistics by intervention group (i.e. numbers and percentages for binary data and means (or medians) and standard deviations (or inter-quartile ranges) for continuous normal (or non-normal) data.

9.8. Safety data

The number and percentage of participants experiencing any adverse events, serious adverse events (SAEs) and suspected unexpected serious adverse reactions (SUSARs) will be presented by treatment arm. A table listing all the SAEs will be provided.

The safety data will also include summaries by treatment arm for:

- Digoxin levels at 6 and 12 months
- Number of patients requiring pacemaker implantation
- Unplanned hospitalisation rates (from the SAE form)
- Number of patients that had pauses and duration of pause (from the 24 hour tape form)
- All cardiovascular events (as recorded in the cardiovascular events form)
- Number of GP visits (from the GP form)

A template for reporting this data is given in Appendix D8.

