No recovery period is required; patients can immediately mobilise after the assessment is complete. Rarely, some patients may exhibit temporary leg/foot paraesthesia which settles spontaneously.

Objectives and analysis:

The objectives of this sub-study are exploratory – our hypothesis is that MSNA will identify a subset of patients with autonomic dysfunction that have an altered or distinct response to rate control therapy.

Change in sympathetic activity from baseline to after treatment with rate control will be analysed in comparison to change in heart rate to understand if sympathetic activity broadly interacts with treatment effects. The results will be used as pilot data to formulate a new research study investigating the role of autonomic dysfunction and outcomes in patients with AF. An analysis plan for this sub-study will be agreed before access to data.

10 Pharmacovigilance

Definitions of different types of AE are listed in **Table 2**. The Investigator should assess the seriousness and causality (relatedness) of AEs experienced by the participant (this should be documented in the source data). For further information please refer to **Section 10.1**.

Table 2: Standard AE Definitions

Term	Definition
Adverse Event (AE)	Any untoward medical occurrence in a patient or clinical trial participant administered a medicinal product and which does not necessarily have a causal relationship with this treatment
Adverse Reaction (AR)	Any untoward and unintended response in a participant to an investigational medicinal product which is related to any dose administered to that participant
Serious adverse event (SAE), serious adverse reaction (SAR) or unexpected serious adverse reaction	Any adverse event, adverse reaction or unexpected adverse reaction, respectively, that: 
 • results in death; • is life-threatening; • requires hospitalisation or prolongation of existing hospitalisation; • results in persistent or significant disability or incapacity; or • consists of a congenital anomaly or birth defect

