10.3 Serious Adverse Events

Refer to Table 2 for definitions

All Serious Adverse Events (SAEs), that are not excluded from expedited reporting will be recorded in the hospital notes and should be reported to the **RATE-AF** Trial Office on a SAE Form. The completed form should be **faxed to the RATE-AF Trial Office on [name] or [name]**, as soon as possible and ideally within one working day of becoming aware of the event. The site Investigator should be able to respond to any related queries raised by the **RATE-AF** Trial Office as soon as possible.

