10.3.1 Expected SAEs NOT to be Reported on a SAE Form

Expected SAEs are those listed in the current SmPC for the trial IMPs and can be excluded from the expedited reporting outlined in **Section 10.1**, for example if they are expected to occur on a regular basis, are no more severe and offer no further new information to the safety profile. These events should continue to be recorded in the source data and relevant CRFs.

In addition, events **NOT** considered to be SAEs are hospitalisations for:

- Routine treatment or monitoring of the studied indication, not associated with any deterioration in condition
- Treatment, which was elective or pre-planned, for a pre-existing condition that is unrelated to the indication under trial, and has not worsened

Note: Death from any cause should be reported on an SAE Form and returned to the **RATE-AF** Trial Office.

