Appendix D7: Feasibility outcomes

Recruitment target of 3 patients per week across all participating centres

To be presented graphically

Compliance and reasons for non-compliance

See section Appendix D3

Number of withdrawals and losses to follow-up (with reasons)

Drop-outs	Digoxin (N=)	Bisoprolol (N=)	Total (N=)
Lost to follow-up			
Withdrawn			
Death			
Total			

List of reason for withdrawals – Digoxin

- 1)
- 2)
- 3)
- ...

List of reason for withdrawals – Bisoprolol

- 1)
- 2)
- 3)
- ...

List of reason for death – Digoxin

- 1)
- 2)
- 3)
- ...

List of reason for death – Bisoprolol

- 1)
- 2)
- 3)
- ...

Drug discontinuation rate and adverse reactions requiring drug discontinuation

Has patient stopped medication due to AE's?	Digoxin (N=)	Bisoprolol (N=)	Total (N=)
No			
Yes			
Missing			
If yes, was it stopped:			
Temporarily			
Permanently			

Cardiovascular Events (from the cardiovascular event form and as identified from the SAE form)

- List of all cardiovascular related events

Number of patients needing therapy-induced requirement for additional treatment

Therapy-induced requirement	Digoxin (N=)	Bisoprolol (N=)	Total (N=)
6 months follow-up			
Did the patient have a pacemaker fitted? No Yes Missing			
If yes: Type of pacemaker Single chamber Dual chamber			
12 months follow-up			
Did the patient have a pacemaker fitted? No Yes Missing			
If yes: Type of pacemaker Single chamber Dual chamber			

Population-specific standard deviations (SD) and proportions

Outcome	6 months			12 months		
	Digoxin	Bisoprolol	Total	Digoxin	Bisoprolol	Total
SF36 PCS N - [SD]						
SF36 MCS N - [SD]						
AFEQT N - [SD]						
LVEF N - [SD]						
E/e' N - [SD]						

Unplanned hospitalisation rates (as recorded from the SAE form)

Unplanned hospitalisation rates	Digoxin (N=)	Bisoprolol (N=)	Total (N=)
No of patients exactly with: 1 unplanned hospitalisation 2 unplanned hospitalisation ... unplanned hospitalisation			
Total number of unplanned hospitalisation			

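### The SAP counts unplanned hospitalisations from the SAE form only, but the protocol lets some expected SAEs stay off that form, so the rate can be too low by an unknown amount that may be nil

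*SAP*

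**What the plan says.** **Source of the rate.** SAP 9.8 gives "Unplanned hospitalisation rates (from the SAE form"), and Appendix D7 gives "Unplanned hospitalisation rates (as recorded from the SAE form"). Neither names a second source. SAP 9.6 lists the same outcome among the feasibility proportions without naming a source and points to D7 for the template.

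**What goes on the form.** Protocol section 10, Table 2 makes an adverse event serious if, among other criteria, it "requires hospitalisation or prolongation of existing hospitalisation". Protocol 10.3 then asks for an SAE form for "All Serious Adverse Events (SAEs), that are not excluded from expedited reporting".

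**What may stay off it.** The next section is headed "10.3.1 Expected SAEs NOT to be Reported on a SAE Form". It says "Expected SAEs are those listed in the current SmPC for the trial IMPs and can be excluded from the expedited reporting", and gives as an example events that are expected regularly, are no more severe and add nothing new to the safety profile. It adds "These events should continue to be recorded in the source data and relevant CRFs". One exception is explicit: "Death from any cause should be reported on an SAE Form".

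**What the rate is for.** Protocol 12.1.3 lists unplanned admission rates under the population-specific proportions, which protocol 3.4 says are collected to allow a sample size calculation for a future trial. SAP 9.8 also uses the rate as a safety summary by arm.

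**The concern.** The two documents use the SAE form for different purposes. In the protocol it is a reporting tool, and some events that add no safety information need not be sent on it. In the SAP it is the only source for counting admissions. A site and a statistician can each follow their document exactly and still leave a recorded unplanned admission out of the rate.

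Naming a single form is not itself the problem. SAP 9.8 also names one form each for pauses and GP visits. For hospitalisation, however, the named form is the one from which the protocol exempts events, and the SAP has no step to recover them.

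At stake are one planning figure and one safety summary. Any omission runs in one direction: the count can only fall. The interval around a pilot estimate does not allow for that.

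**Working it through.** The documents state no hospitalisation rate, so there is no figure to reproduce. The check is a comparison of the texts, followed by simple arithmetic on an assumed omission share.

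**Following one admission through the documents**

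1. A participant has an unplanned admission for an effect listed in the SmPC of the allocated drug. Under Table 2 this is an SAE.
2. Under protocol 10.3 it goes on an SAE form only if it is not excluded from expedited reporting.
3. Under 10.3.1 it may be excluded, provided it is not a death. The site then records it in source data and the relevant CRFs.
4. Under SAP 9.8 and D7 the statistician counts from SAE forms. The admission is not counted.

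**Admissions this does not affect.** Admissions for events not listed in the SmPC still go on the form, and so do all deaths. The hospitalisations that 10.3.1 treats as non-SAEs are routine care of the studied indication without deterioration, or elective and pre-planned treatment. Leaving those out of an unplanned rate is not an undercount.

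**Size.** Let *f* be the share of unplanned admissions left off the form. The documents give no value, so the values below are assumptions. For the total number of admissions, reported count / true count = 1 − *f*:

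| assumed *f* | reported as a share of true |
|---|---|
| 0% | 100% |
| 10% | 90% |
| 25% | 75% |
| 50% | 50% |

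D7 also tabulates patients with exactly one, two or more admissions. Those rows need not shrink by the same share: a patient with several admissions drops out only if all were left off, and otherwise moves to a lower row.

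**By arm.** If the share differs between arms, the digoxin/bisoprolol ratio of admission counts is multiplied by (1 − *f*_D)/(1 − *f*_B). With assumed shares of 10% and 30% this is 0.90/0.70 = 1.29; with the shares reversed it is 0.70/0.90 = 0.78; with equal shares it is 1.00. Expectedness is judged against a separate SmPC for each drug (protocol 10.1), so unequal shares are possible. Nothing in the documents shows that they occur.

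**The case against.** **The exemption may be narrow or unused.** It is permissive, and its example refers to events that are regular and no more severe. Table 2 ties expectedness to severity as well as nature, so a listed effect bad enough to need admission may fall outside it. Protocol 11.5, Table 5 lists the SAE form for faxing within 24 hours without mentioning the exemption. Sites may have sent a form for every admission. All of this stands, and it is why the loss may be nil. It does not remove the gap, because capture then depends on each site's choice and the SAP would not reveal what was left out.

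**The exemption may concern speed of reporting only.** The heading of 10.3.1 is about the form itself, 10.3 makes the form conditional on non-exclusion, and the separate instruction on deaths would be unnecessary if every expected SAE went on the form anyway.

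**Other sources exist.** Protocol 9.8 treats the best way to obtain hospitalisation data as an open feasibility question and counts hospitalisation among the cost drivers. Optional data linkage and the 2- and 5-year follow-up could also check admissions later, in participants who consent. These are real resources, but SAP 9.8 and D7 do not draw on them for this rate.

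**Stronger readings that do not hold.** A reader might infer from protocol 10.1, which anticipates that most adverse events and reactions will be expected, that most admissions are lost. That sentence concerns treatment-related toxicities and says nothing about the causes of unplanned admissions. A reader might also infer that the SAE tables in Appendix D8 are short for the same reason. SAP 9.8 promises a listing of all SAEs, and neither it nor D8 ties that listing to the form.

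**Conclusion.** The conflict between the documents is real: followed as written, they can give an unplanned hospitalisation rate that is too low. The size is unknown and may be zero. It depends on how many unplanned admissions are for SmPC-listed effects and how often sites used the exemption, and the documents give neither.

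The consequence is limited to description. SAP 9.6 plans no model-based analysis of the feasibility outcomes, and no primary or secondary efficacy result depends on this count. A reader might conclude that the comparison between arms is biased; unequal loss is possible but not shown.

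A reader might also conclude that the future trial would be mis-sized by a definite amount. The documents give no admission rate, target effect or power for that trial. A low pilot rate would enlarge a trial designed around a fixed relative reduction only if that trial captured admissions more completely than this one. This is a data-source correction worth making because it is cheap.

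**What to change.** In SAP 9.8 and Appendix D7, replace the words that name the SAE form as the source with: *from SAE forms plus unplanned admissions recorded in the relevant CRFs or source data under protocol 10.3.1 and on the cardiovascular events form, de-duplicated and ascertained the same way in both arms*. D7 already sets the precedent, since it combines the cardiovascular event form with the SAE form for cardiovascular events.

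Report by arm how many unplanned admissions had no SAE form. That number shows directly whether the undercount would have been nil, small or unequal.

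The protocol's reporting exemption can stay as it is, and the D8 tables need no change. The cost is an edit to the SAP and a small merge of records that protocol 10.3.1 already asks sites to keep. The CRFs are not among the documents; if they do not flag admissions, a source-data query limited to the exempted events is also needed.
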